6.2. INVESTIGATIONAL PRODUCT SUPPLIES, STORAGE AND ACCOUNTABILITY

6.2.1. Investigational Product Supplies

CX-4945 will be supplied by Senhwa Biosciences. Study sites will receive CX-4945 prior to enrollment of the first patient. The clinical site pharmacy /qualified staff member will dispense the supplies to the patients enrolled to the treatment Arm A in quantities appropriate according to the study visit schedule. Any unused product or waste material should be disposed of in accordance with local requirements.

[REDACTED]

[REDACTED]

[REDACTED]

6.3. CONCOMITANT MEDICATION

[REDACTED]

[REDACTED]

[REDACTED]

[REDACTED]	[REDACTED]
[REDACTED]	[REDACTED]
[REDACTED]	[REDACTED]

[figure not shown]
[REDACTED]

[REDACTED]

[REDACTED]

6.4. CX-4945 DRUG INTERACTION

A black and white image showing a large, dark, irregular shape in the center, possibly a redacted area. The shape is surrounded by a white border. The image is framed by a thick black border.

7. STUDY COMPLETION OR DISCONTINUATION

7.1. PATIENT COMPLETION

A patient is considered to have completed the study if he or she has completed the treatment phase and Follow-up visits at Day 28, Day 45, and Day 60.

Discontinuation from CX-4945 does not mean the withdrawal from the study assessments. Patients who discontinued therapy should remain in the study and continue follow-up for key outcomes. The only reasons for study withdrawal are withdrawal of consent from further participation in the study and loss to follow-up.

7.2. PATIENT WITHDRAWAL FROM PARTICIPATION IN THE STUDY

At any point during the study all patients have the right to withdraw consent from further participation in the study refusing to complete scheduled study assessments and follow-ups without prejudice to future care. If the patient refuses further visits, the patient should continue to be followed unless the patient withdraws consent for disclosure of future information or for further contact. In this case, no further study-specific evaluations should be performed and no additional data should be collected. The sponsor/investigator may retain and continue to use any data collected before such withdrawal of consent.

Another reason for withdrawal from study is loss to follow-up. Before a subject is identified as lost-to-follow up, the site should make all reasonable efforts to contact the subject. These attempts must be documented and should include at a minimum one phone call and one certified letter.

The reason for withdrawal from the study will be recorded in the subject medical records.

7.3. PATIENT DISCONTINUATION FROM STUDY TREATMENT

Patients may withdraw from treatment at any time at their own request, or they may be withdrawn at any time at the discretion of the investigator/sponsor for safety or behavioral reasons, or the inability of the patient to comply with the protocol-required schedule of study visits or procedures at a given investigator site.

All patients who discontinued from study treatment but maintain consent, should remain in the study through the end of the study period for all important safety and anti-viral activity assessments.

Investigators considering patient withdrawal from study treatment should contact the medical monitor prior to such discontinuation. Patients who have study treatment discontinued will continue to be followed, per protocol, whenever possible. If visits to the site are not possible,

subjects can be followed via telehealth or other approaches (telephone calls, e-mails, and texts to ascertain vital status in all patients.

Patients who have study treatment discontinued due to a serious adverse event will be followed until study completion, resolution or stabilization of the event (whichever occurs later).

Reasons for withdrawal of study treatment may include:

- Patient refused further treatment
- Pregnancy
- Unacceptable toxicity
- Significant study therapy non-compliance
- If any clinical adverse event (AE), laboratory abnormality, or other medical condition or situation occurs such that continued participation in the study would not be in the best interest of the participant
- Disease progression which requires discontinuation of the study intervention
- If the participant meets an exclusion criterion (either newly developed or not previously recognized) that precludes further study participation

8. STUDY ASSESSMENTS AND PROCEDURES

The study will have three phases: Screening Phase/Visit, Treatment Phase, and Follow-Up Phase. A schedule of assessments and procedures is provided in **Section 1.3**.

Due to the risk of infection for study staff and hospital personnel, the site may take steps to limit face-to-face interaction (i.e., telehealth or eSignature).

8.1. STUDY PROCEDURES

8.1.1. Screening Period:

The patient will sign and date the informed consent form (ICF) and Health Insurance Portability Accountability Act (HIPAA) authorization (according to site policy and practices) prior to any study-related procedures. The study center will maintain the study-specific screening and enrollment logs at their site.

For screening procedures see the Schedule of Activities in **Section 1.3** and Assessments in **Section 8.2**.

8.1.2. Treatment Period:

For the treatment period procedures see the Schedule of Activities in **Section 1.3** and Assessments in **Section 8.2**.

Patients who meet the eligibility criteria and are randomized will have completed the following evaluations and assessments on Day 1 prior to treatment: review of any changes in medication history, physical examination, vital signs, clinical status – ordinal scale assessment and COVID-19-related symptoms scale assessment, EQ-D5-5L questionnaire, pulse oxygen saturation (SpO₂), Nasopharyngeal Swab Sample Collection (for quantitative virologic testing viaRT-PCR), laboratory sample collection for routine serum biochemical, hematologic, coagulation, IL-6 levels and CRP, LDH, CPK, ferritin, D-dimer analysis.

During the treatment phase, patients randomized to the treatment arm A will receive CX-4945 (1000 mg) twice a day for up to 14 days. Details on CX-4945 administration can be found in **Section 6**.

8.1.3. Follow Up Period

For follow-up procedures see the Schedule of Activities in **Section 1.3** Assessments in **Section 8.2**.

8.1.4. Unscheduled Visits

In the event that the patient will return to clinic at a time other than a regularly scheduled study visit, the visit will be regarded as an unscheduled visit. Assessments at unscheduled visits are at the discretion of the Investigator. All pertinent findings, including adverse events or changes in medications, will be noted in the patient medical records.

8.2. ASSESSMENTS

Every effort should be made to ensure that the protocol-required tests and procedures are completed as described. However, it is anticipated that from time to time there may be circumstances outside of the control of the investigator that may make it unfeasible to perform the test. In these cases the investigator will take all steps necessary to ensure the safety and well-being of the patient. When a protocol-required test cannot be performed, the investigator will document the reason for this and any corrective and preventive actions that he or she has taken to ensure that normal processes are adhered to as soon as possible. The study team will be informed of these incidents in a timely manner.

For samples being collected and shipped, detailed collection, processing, storage, shipment instructions and contact information will be provided to the investigator site prior to initiation of the study.

8.2.1. Safety Assessment

Safety assessments will include collection of adverse events (AEs), serious adverse events (SAEs), vital signs and physical examination, electrocardiogram (ECG [12-lead]), laboratory assessments, including pregnancy tests and verification of concomitant treatments.

8.2.1.1. Pregnancy Testing

All pregnancy tests used in this study, either urine or serum, must have a sensitivity of at least 25 mIU/mL and must be performed by a certified laboratory. For female patients of childbearing potential, a negative pregnancy test is required before receiving CX-4945 (1 negative pregnancy test at screening). Following a negative pregnancy test result at screening, appropriate contraception must be commenced. The patient should have used 2 forms of contraception. Pregnancy tests will also be repeated at Day 14/EOT to confirm that the patient has not become pregnant during the study. Pregnancy tests will also be done whenever 1 menstrual cycle is missed during the study and when potential pregnancy is otherwise suspected. In the case of a positive confirmed pregnancy, the patient will be withdrawn from administration of investigational product but may remain in the study.

8.2.1.2. Adverse Events (AEs)

Assessment of AEs will include the type, incidence, severity (as graded by a Toxicity Grading Scale for Healthy Adult and Adolescent Volunteers Enrolled in Preventive Vaccine Clinical Trials (<https://www.fda.gov/media/73679/download>)) timing, seriousness, and relatedness. For AE assessment details, see **Section 8.3.3.** Investigator will follow-up for any AEs/SAEs and mortality status at Day 28, Day 45 and Day 60.

8.2.1.3. Vital Signs and Physical Examination

Patients will have a full physical examination to include an examination of all major body systems, height (at screening only), weight, blood pressure and pulse rate, which may be performed by a physician, registered nurse or other qualified health care provider, as acceptable according to local regulation. Symptom-directed physical examination should be limited to systems of primary relevance (i.e., cardiovascular, respiratory, and systems associated with symptoms). Changes from baseline abnormalities should be recorded at each subsequent physical examination. New or worsened abnormalities should be recorded as an AE.

Pulse oximetry should be collected prior to collection of the blood pressure, pulse rate, and temperature. Oxygen levels should be evaluated on the finger in accordance with the site's standard procedures. All abnormalities will be evaluated by the study physician.

Blood pressure, heart rate, respiration rate, and temperature should be recorded after approximately 5 minutes rest. An abbreviated physical exam is an assessment for emergent toxicities or changes from prior visits and a symptom directed exam conducted by a physician, trained physician's assistant or nurse practitioner, as acceptable according to local regulation.

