3. STUDY OBJECTIVES AND ENDPOINTS

Primary Objective	Primary Endpoint
To assess safety and tolerability of CX-4945 administered orally BID to patients with moderate COVID-19	
Adverse events occurring from randomization (Day 1) to Day 60 (including vital signs, physical findings, clinical laboratory, and ECG results) as characterized by type, frequency, severity [(as graded by Toxicity Grading Scale for Healthy Adult and Adolescent Volunteers Enrolled in Preventive Vaccine Clinical Trials (https://www.fda.gov/media/73679/download)], timing, seriousness, and relationship to study therapy.
Secondary Objectives	Secondary Endpoints
To compare time to normalization of COVID-19-related clinical signs in CX-4945 treatment arm versus the control arm.	
Number of days from Randomization (Day1) to the day when the following clinical signs are back to normal as evaluated at every visit during the treatment period (Day 1, Day 4, Day 8, Day 11 and Day 14) and at Follow-up visits on Day 28 and Day 45 :
 
Fever is $\leq 36.6^{\circ}\text{C}$ from axillary site, or $< 37.2^{\circ}\text{C}$ from oral site or $< 37.8^{\circ}\text{C}$ from rectal or tympanic site)Respiratory rate is < 20 bpm while breathing room air at sea level$\text{SPO} \geq 96\%$ in room air without shortness of breath or dyspneaHeart rate < 90 beats per minute 
Note: If some signs listed above were caused by other conditions documented in the medical history and started before COVID-19, the patient can be considered as recovered, when these signs return to the previous (pre-COVID-19) values.

To compare duration of COVID-19-Related clinical symptoms in CX-4945 treatment arm versus the control arm.	Number of days from Randomization (Day1) to the day when: 
No key COVID-19-related symptoms scored higher than 1 as documented using a Patient Reported Outcome (PRO) instrument (a Patient Diary for Assessment of Common COVID-19-Related Symptoms – see Appendix 3),

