8.3.1. Definitions of AE

An AE is defined as any unfavorable or unintended sign, symptom, or disease that occurs or is reported by the patient to have occurred, or a worsening of a pre-existing condition. An AE may or may not be related to the study treatment.

AEs will be elicited through direct questioning and patient reports. Any abnormality in physical examination findings or laboratory results that the investigator believes is clinically significant (CS) to the research patient and that occurred after initiation of the first study treatment will be reported as AEs. Abnormal findings that are NOT clinically significant should not be recorded as an AE.

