8.3.3. Classification of AEs

8.3.3.1. Severity of AE

As study population is outpatients with moderate COVID-19, a standardized toxicity grading scale is modified to reflect the study population. Toxicity Grading Scale for Healthy Adult and Adolescent Volunteers Enrolled in Preventive Vaccine Clinical Trials will be used for grading AEs associated with systemic (general) abnormalities, vital signs, illnesses and lab abnormalities. Full guidelines may be obtained at <https://www.fda.gov/media/73679/download>.

Table 6. Toxicity Grading General Guidelines

Grade	Description
Grade 1	Mild; No interference with activity
Grade 2	Moderate; Some interference with activity not requiring medical intervention
Grade 3	Prevents daily activity and requires medical intervention
Grade 4	Potentially Life-threatening ER visit or hospitalization
Grade 5	Death related to AE.

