9.5. BLINDING

This is an open label study.

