Days to first response = date of first response – the first treatment date/time + 1

Days to last observation = date of last evaluation – the first treatment date/time + 1

For Arm SOC, the first treatment date is the date of visit 2

- (6) For Clinical Relevance
 

CS: abnormal and clinically significant	LLN: lower limit of normal range
NCS: abnormal but not clinically significant	ULN: upper limit of normal range
- (7) For Transition of Clinical Relevance
 

Relieved	CS (Medical History or Adverse Event) at baseline to Normal / NCS at visit.
Unchanged	Including Normal at baseline to NCS at visit, NCS at baseline to Normal at visit.
Worsened (Medical History)	Normal / NCS at baseline to CS (Medical History) at visit
Worsened (Adverse Event)	Normal / NCS / CS (Medical History) at baseline to CS (Adverse Event) at visit

If both 'Medical History' and 'Adverse Event' are checked for 'CS', it will be counted as 'Adverse Event' only.

- (8) Abbreviations of Statistics
 

N: number of non-missing values	ANOVA: analysis of variance
M: missing, not available	ANCOVA: analysis of covariance
Missing: number of missing values	CHISQ: Chi-Square test
Mean: mean of values	FISHER: Fisher's exact test
SD: standard deviation of values	MHCHISQ: Mantel-Haenszel chi-square test on given scores
Q1: 25% quartile of values	T: two sample t test
Q3: 75% quartile of values	W: Wilcoxon rank-sum test
Median: median of values	Diff.: difference
IQR: inter-quartile-range (IQR=Q3-Q1)	
Min: minimum of values	
Max: maximum of values	
CI: confidence interval	
LS-mean: least-square mean	

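### Two protocol sections give incompatible rules for recording a new, non-significant examination finding as an AE, and no SAP table grades measured values independently of the unblinded significance call

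*Protocol*

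**What the plan says.** The primary endpoint (Protocol section 3) is adverse events from Day 1 to Day 60, explicitly including vital signs, physical findings, laboratory and ECG results, described by frequency and severity among other features.

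Two sections say when an examination finding becomes an AE:

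- Protocol 8.2.1.3: "New or worsened abnormalities should be recorded as an AE". No condition of clinical significance is attached. The section places weight, blood pressure and pulse rate within the full physical examination.
- Protocol 8.3.1: an abnormal examination finding or laboratory result is reported as an AE if the investigator believes it is clinically significant (CS). It adds: "Abnormal findings that are NOT clinically significant should not be recorded as an AE".

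On assessment, Protocol 9.5 states: "This is an open label study". On severity, Protocol 8.3.3.1 says the named vaccine-trial toxicity scale "will be used for grading AEs associated with systemic (general) abnormalities, vital signs, illnesses and lab abnormalities".

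The SAP works with the significance categories. Its Instructions and Abbreviations, item (6), has "NCS: abnormal but not clinically significant". Item (7) defines the transition category Unchanged as "Including Normal at baseline to NCS at visit, NCS at baseline to Normal at visit".

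**The concern.** AE frequency is the primary outcome, so the rule that admits a finding to the AE count should be single and the same everywhere. Here a new NCS examination finding is an AE under one section and barred under the other. The SAP plans for two sites, and nothing stops them from following different sections. Under 8.3.1 the decision is also a judgement made with the arm known. An investigator who expects toxicity in Arm A could call a borderline finding CS there and NCS in Arm B, or the reverse. A severity display that does not pass through that judgement would help a reader see whether this had happened.

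**Working it through.** There is no plan figure to reproduce: Protocol 9.3 states that no power calculation was made. The check is mainly a comparison of the texts.

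**1. Can both rules be followed?**

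| New or worsened finding | Protocol 8.2.1.3 | Protocol 8.3.1 |
|---|---|---|
| Examination finding, judged CS | AE | AE |
| Examination finding, judged NCS | AE | Not an AE |
| Laboratory result, judged CS | No rule | AE |
| Laboratory result, judged NCS | No rule | Not an AE |

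Only the second row conflicts. The laboratory rows have one rule, which rests on judgement.

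**2. Does another passage say which section governs?** Protocol 8.3 refers to the AE definition provided in the protocol as a whole. Protocol 8.2.1.2 points to 8.3.3, which covers classification and not whether to record. The SAP presupposes the 8.3.1 rule by separating NCS from CS (Adverse Event), but it does not amend 8.2.1.3.

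**3. What does the SAP show regardless of AE status?**

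- Table 14.3.7: examination abnormalities by body system, visit and arm, split into NCS, CS (Medical History) and CS (Adverse Event).
- Laboratory layouts under 14.3.2 to 14.3.6: the same split, with values and changes from baseline by arm for continuous tests.
- Table 14.3.8: normal or abnormal by fixed limits for temperature, respiratory rate, heart rate and SpO2.
- Tables 14.3.1.1, 14.3.1.4 and 14.3.1.5: treatment-emergent AEs at Grade 3 or above, Grade 4 and Grade 5.

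**4. Does any of these grade all measured values?** No.

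- The graded tables contain only findings already recorded as AEs.
- The NCS/CS split is itself the unblinded judgement.
- The 14.3.8 limits match the SAP's efficacy limits for normalization of signs and are not toxicity grades. Blood pressure has none. Inclusion criterion 3 requires respiratory rate of at least 20 or heart rate of at least 90, so every eligible patient is already abnormal on one of these when eligibility is assessed. A two-level flag cannot show worsening from there.
- Means, medians and ranges do not count patients reaching a grade or shifting from a baseline grade.

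**5. Scale of one decision.** Inputs: about 20 patients, 1:1 (Protocol 9.3), so about 10 per arm. One patient reclassified = 1/10 = 10 percentage points, provided the finding is that patient's only event in the row being counted. Exact (Clopper-Pearson) 95% limits are 2.5% to 55.6% for 2/10 and 6.7% to 65.2% for 3/10.

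**6. Illustration of differential recording (assumed values, not from the documents).** Let t be the true proportion of patients with such a finding, equal in both arms, and let cA and cB be the shares recorded. Spurious difference = t × (cA − cB).

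| t | cA = 1, cB = 0.75 | cA = 1, cB = 0.50 | cA = cB = 0.50 |
|---|---|---|---|
| 0.30 | 7.5 points | 15 points | 0 |
| 0.50 | 12.5 points | 25 points | 0 |
| 0.70 | 17.5 points | 35 points | 0 |

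With equal under-recording there is no spurious difference, but incidence is understated in both arms.

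**The case against.** The best defence is that the conflict is a narrow slip of wording. The AE section is the natural home of the definition, the SAP applies it consistently, and nothing shows that sites used two rules. The SAP displays NCS findings by arm, so an imbalance in CS calls would be partly visible. The expected drug-related events are mainly gastrointestinal (Protocol 6.1.5). As symptoms, these reach the AE record through questioning and patient report, and SAEs have their own criteria. The AE tables carry no p-values. The endpoint promises grades for AEs, not for every measurement, so the missing grade tables breach nothing stated.

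Most of this stands, and it limits the point. A reader might infer that the trial has no objective check on AE recording, or that the whole primary endpoint rests on unblinded opinion. The documents do not support either reading: the displays in step 3 of the working exist, and the contradiction is confined to examination findings.

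A reader might also try to turn the conflict into a number of lost AEs, starting from 20 patients × 4 post-Day 1 examinations in Table 14.3.7 = 80. That is a ceiling. Recovered patients may be followed remotely, post-baseline examinations are symptom-directed, a persisting finding is one event, and no rate of NCS findings is given.

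Two things survive. No text resolves the conflict, and none of the existing displays gives severity independently of the CS/NCS decision.

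**Conclusion.** The concern holds in limited form. Protocol 8.2.1.3 and 8.3.1 cannot both be followed for a new examination finding judged NCS, including the measurements that 8.2.1.3 places within the examination. For laboratory results the issue is unblinded judgement under a single rule. The SAP adds useful displays but no toxicity grading of all measured values. The size of any distortion cannot be derived from the documents. The only firm figure is 10 percentage points of an arm's incidence per reclassified patient, assuming 10 per arm and no other event for that patient in the same row. The recording shares in the illustration are assumptions. This is a correctable ambiguity and a missing safeguard; it does not make the trial invalid.

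**What to change.** 1. Reconcile Protocol 8.2.1.3 and 8.3.1 into one AE-recording rule, applied identically in both arms and at all sites. A cross-reference from one section to the other would be enough.
2. Add to SAP 14.3.2 to 14.3.5 and 14.3.8 a by-arm table of worst post-baseline toxicity grade, with shift from baseline grade. Compute it by program from the recorded laboratory and vital-sign values regardless of the NCS/CS tick, for the parameters covered by the scale the protocol already names.

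Cost: one protocol sentence and some programming time, with no new data. The tables can still be added before database lock, the point by which Protocol 9.8 requires the SAP to be approved. Parameters the scale does not cover stay ungraded. Appendix 2 gives the scale only by link, so its coverage and thresholds must be confirmed from the scale itself.
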